implementation. VA Risk ID IAU was made available to all VHA facilities starting in July 2018. Each facility was required to identify a Facility Champion, who accesses the implementation support system and disseminates information regarding tools, training, technical assistance and quality assurance to their facility. **Proactive TA** is delivered via weekly conference calls and a support email address. These resources facilitate proactive, rather than reactive, problem-solving with the field .³¹⁻³² When indicated, we also offer phone calls with individual providers or teams to collaboratively identify flexible implementation solutions that will allow fidelity to be maintained, a common implementation challenge³². IAU also includes a SharePoint site which houses a variety of tools developed for VA Risk ID (e.g., guidance documents, education about VA Risk ID, Discussion Board to encourage a community of learning). Our team also conducted a three-part webinar series, offering *training* on the overall strategy and practice components. These live webinars were converted into trainings in the VA Talent Management System (TMS) so that employees could access them after the live webinar series. Finally, a fallout report was developed for *quality assurance*. This report provides information about patients who did not receive indicated levels of the screening and evaluation process (e.g., secondary screen not completed after a positive primary screen). **b. Audit & Feedback (A/F):** A/F will serve as the first stage implementation intervention for sites that do not meet the benchmark for adequate implementation following 6 months of IAU. The A/F intervention will be guided by the model of actionable feedback17 and other identified best practices20. The following components will be incorporated into the A/F design and delivery: i) individualized performance data (site level), ii) frequent delivery intervals (monthly), iii) comparisons with other sites, iv) graphical and text form displays of information, v) constructive, non-punitive tone, vi) target performance or benchmark provided, and vii) specific actions or recommendations for meeting the target. The audit component will include the clinical performance measures for the different VA Risk ID practices. These measures will be gathered monthly along with more detailed information from the fall out reports. A/F reports will be delivered monthly to the PC group practice manager and local manager with oversight of PCMHI. Various prototypes will be user-tested during the Run-In Phase and feedback from potential end users will be obtained to develop a final prototype for use during the Phase I intervention. Further refinements may be made to the prototype and other aspects of intervention delivery based on feedback obtained from sites receiving the A/F intervention during Phase I evaluation. [name], nationally recognized expert in A/F interventions, will provide ongoing consultation and guidance on the A/F intervention for this project. c. External Facilitation (EF): The facilitation approach proposed for this study is grounded in the i- PARIHS framework²⁵ described above. The *recipients* of VA Risk ID (i.e., the *innovation*) include providers, teams and local leadership. Facilitation will involve gaining an understanding of these recipients' key characteristics such as: motivation, values and beliefs, goals, skills and knowledge, time, resources and support, and power and authority²⁵. Facilitators will also learn about the *inner and outer* contexts of the recipients. The inner context includes the immediate setting for implementation (e.g., the clinic in which they work) and organization in which the clinic is embedded (e.g., VA medical center). The outer context is the VHA and the related policies, regulatory frameworks and political environment that impact its functioning²⁵. Facilitation will be conducted by a team of facilitators who will employ the facilitation process (a set of strategies and actions) to improve uptake of VA Risk ID by the recipients. Given that it is unlikely that sites have an internal facilitator who is well-versed in implementation knowledge and skills^{24,33}, we will utilize EF. External facilitators will be trained and mentored by an expert facilitator ([name]) utilizing a QUERI-supported manual and two-day in-person training developed by [name] and colleagues to guide IF efforts in VHA²⁴. EF will occur with A/F during Intervention Phase II. To ensure successful implementation, external facilitators will flexibly deliver the facilitation process utilizing an integrated set of implementation strategies (e.g., stakeholder engagement, identification of barriers and facilitators, education, problem solving, the use of formative data, communication, and ongoing support).

C7. Analyses. a. Sample Size and Power Calculations: Power was calculated using the two-sample ttest procedure in Power and Sample Size (PASS 16). As there are two primary EPRP outcomes (sui2 and csra1), alpha is set to 0.025. The FY2018 first quarter numbers for a similar EPRP (sre1, timely SRE if positive PTSD or MDD screen) across 140 facilities was used to obtain an estimated standard deviation for sui2 and csra1 of 0.10. Power was calculated for two scenarios given the preliminary fallout data noted above. Assuming proportions of 0.8 and 0.9 not adequately implementing at month 6 of the run-in phase such that N=112 and N=126 are eligible for randomization at R1, this would provide 80% power to detect a difference in change between A/F and IAU of 0.059, and 0.055, respectively. Regarding secondary aim 1, assuming alpha=0.05, SD=0.10, and facilities eligible for randomization at R2 of 56 and 63, there is 80% power to detect a difference in change between continued A/F and A/F + Facilitation of 0.076 and 0.072, respectively. Given the same assumptions for secondary aim 2 as used for secondary aim 1, the detectable differences in change are the same for examining continued A/F versus discontinued A/F. **b. Primary Aim:** Using linear regression, the primary

EPRP outcomes of change in sui2 and csra1 from the 6th month of the baseline period to the 10th month of the first interventional phase will each be modeled as a function of group (A/F vs. IAU), the baseline outcome value, the stratification variables of facility complexity (high, medium, low) and baseline performance level (above or below the median average fallout rate), and geographic region (West, Midwest, Southwest, Southeast and Northeast). Inference will be made based on the coefficient associated with the group variable and 97.5% confidence intervals (CI) will be reported (alpha=0.025). A similar analysis will be used to determine the effect of A/F on the change in the EPRP outcome for the primary screeners (sui40 and sui51), with 95% CIs reported. **c.** Secondary Aims: 1). To test the effect of the addition of EF for those who do not implement adequately at end of interventional phase 1, the primary EPRP outcomes of change in sui2 and csra1 from the 10th month of interventional phase 1 (baseline for interventional phase 2) to the 10th month of interventional phase 2 will be modeled as a function of group, the baseline outcome value, the stratification variables and geographic region (if sample sizes allow for control of this variable). Inference will be made based on the coefficient associated with the group variable and 95% CIs will be reported. A similar analysis will be used to determine the effect of the addition of EF on the change in the EPRP outcome for the primary screeners (sui40, sui51), with 95% CIs reported. 2). An analysis similar to that described for secondary aim 1 will be employed to investigate the effect of discontinuing A/F for those who implemented adequately at the end of interventional phase 1. Lastly, we will use a data driven approach to characterize each of the four EPRP outcomes over time for each group outlined in Figure 2 (group 1-6). Mixed effects models with a random intercept and slope will be used to model each of the four EPRP outcomes as a function of categorical group (1-6) and an interaction between group and a Bspline transformation on time (allowing the outcome to vary smoothly over time, using 21-time points, i.e., the 6th baseline month and every month of each interventional phase) such that each group will have its own trajectory. The trajectory for each group will be plotted with pointwise confidence intervals. **d. Exploratory** Aims: *i. Reach*: Reach will be calculated using the following formula: actual number of Veterans screened or evaluated/ actual number of Veterans eligible for screening, calculated cumulatively across all three study phases and all sites. We will calculate reach for each assessment stage of VA Risk ID. We will examine representativeness of patients reached by comparing demographic characteristics and other relevant variables (e.g., settings in which screening was completed) between eligible Veterans who were screened and/or evaluated and those who were not. Given that Veterans are clustered within facility, if the intra-class correlation between Veterans within each facility is estimated to be greater than zero, methods appropriate for clustered data will be employed to compare the variables of interest. For continuous variables, linear mixed models will be used with a random facility effect and non-normal data will be transformed. For binary variables, generalized linear mixed models will be used with a logit link and for categorical variables, random effects multinomial models will be employed. If the ICC is zero, t-tests, Wilcoxon rank-sum, Chi-square or Fisher's exact tests will be used, as appropriate. *ii. Adoption & Implementation Factors:* Key informant interviews will be used to examine factors influencing adoption of the implementation interventions and barriers and facilitators of implementing VA Risk ID to fidelity. All qualitative data sources, including interview transcripts and documents will be compiled and managed using Nvivo V. 9.0 software. We will take a general inductive approach³⁴. Specifically, data analysis will be determined by both the research objectives (i.e., domains of the RE-AIM framework) and multiple readings and interpretation of the raw data (i.e., content analysis). The goal is to establish clear links between the research objectives and the summary findings derived from the raw data. *iii. Effectiveness- Clinical Innovation:* We wish to examine whether Veterans who receive the CSRE are more likely to receive a safety plan within 2 weeks than those who screen positive on the primary screen only. To account for clustering of Veterans within facility, a mixed-effects logistic regression will be used to model the outcome of safety plan within 2 weeks (yes/no) as a function of group (receipt of CSRE/positive on primary screen only) with a random subject within facility effect. Additionally, to determine if receipt of a timely safety plan depends on whether Veterans are considered to be at low, moderate or high acute risk of suicide, this model will be repeated with the addition of a group by (categorical) acute risk interaction. Odds ratios for receipt of CSRE relative to positive on primary screen only will be reported for each level of acute risk with 95% confidence intervals.

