C5. Randomization. **a. Primary Tailoring Variable (PTV):** The PTV determines the set of randomized intervention options. Thus, the PTV in any SMART must be a proximal measure of the outcome that denotes early success or failure and can be implemented in practice²⁸. In this SMART, the PTV is a predetermined benchmark for adequate implementation. This benchmark will be based on C-SSRS Screener fallouts and CSRE fallouts. The cut-off for both must be 80% or higher (i.e., less than 20% fallouts) to be considered adequate implementation. This cut-off was chosen with input from the program partner and previous QI projects with the program office that involved setting implementation benchmarks (i.e., REACH VET implementation). This benchmark is meant to represent a performance target that all facilities are expected to work towards. Preliminary data indicates that, across facilities since October 2018, the 1st quartile of C-SSRS fallouts is 47.9% (range: 12.9% - 87.4%), and the 1st quartile of the CSRE fallouts is 61.2% (range: 12.5% - 100%). 75% of sites currently have C-SSRS and CSRE fallout percentages greater than 47.9% and 61.2%, respectively. Based on these numbers at least 80-90% of sites currently do not meet criteria for adequate performance. We expect that this number to decrease some as implementation continues, but we expect that many sites will still have significant room for improvement when this project begins. The program partner may adjust this benchmark based on additional data gathered. **b.** Randomization procedures: Randomization will occur at the site level. VAMCs that are not meeting the benchmark for adequate implementation (See PVT above) at Baseline month 6 will be randomized 1:1 (R1) to receive A/F or continued IAU for 10 months. A/F sites that do not meet the benchmark for adequate implementation at the 10th interventional month will be randomized 1:1 (**R2**) to either continue A/F or augmentation with EF (A/F + EF) for an additional 10 months. A/F sites that meet the criteria for adequate implementation will be randomized 1:1 (**R3**) to either continue A/F or discontinue A/F and return to IAU. R1 will be stratified by facility complexity level (i.e., high, medium and low) and level of performance (i.e., low or moderate) at baseline. The Facility Complexity Model²⁹ classifies VA medical facilities at levels 1a, 1b, 1c, 2, or 3. Level-1a facilities are the most complex and level-3 facilities are the least complex. Levels 1a-1c will be considered high complexity, level 2- medium complexity and level 3- low complexity. Approximately 61% of facilities (N=85) are high complexity, 17% (N=24) are moderate and 22% (N=31) are low complexity. Additionally, the average of the C-SSRS Screener and CSRE fallout rates for the 6th Baseline month will be calculated for each facility to be randomized (R1) and the median of these averages will be used to determine stratification by level of performance (i.e., low – above median fallout rate, or moderate – below median fallout rate). R2 will also be stratified by facility complexity level and level of performance (based on the median of the fallout rate at the 10th month of phase 1). R3 will be stratified only by facility complexity level as all sites will have met the benchmark. These procedures will ensure that intervention groups are balanced for site variables that may correlate highly with outcomes. If less than 12 sites will be randomized at R2, stratification will only occur based on facility complexity, unless all facilities are at the same level of complexity in which case only median level of performance will be used for stratification.

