Examining the Effectiveness of an Adaptive Implementation Intervention to Improve Uptake of the VA Suicide Risk Identification Strategy (PEC 19-303)

NCT04243330

October 17, 2024

QUERI RISK ID Statistical Analysis

Primary Aim. Determine if the addition of Audit and Feedback in Phase 1 (February 2021 – November 2021) significantly improved eCSSRS1 and eCSRE1 adherence. To determine the effect of Audit & Feedback on Phase 1, we compared group 6 (Implementation As Usual [IAU] in Phase 1; N=66) to Groups 2, 3, 4, and 5 combined (Audit & Feedback [AF] in Phase 1; N=67). We used all available data and modeled monthly 1) eCSSRS1 and 2) eCSRE1 adherence across the entire study period (January 2021 – March 2024) for each group (IAU and AF). We chose to estimate these trajectories using natural cubic B-spline transformations on time to allow for smoothly changing trajectories and not restrict the estimation to a parametric form (e.g., polynomials). Internal knot selection for the B-splines was based on visible change points in descriptive longitudinal plots – these were November 2021, January 2022, November 2022, and March 2023 (or months 11, 13, 23, and 27). These 4 internal knots result in 5 knot spans and 5 degrees of freedom for each group/outcome combination modeled. Each outcome was then modeled as a function of group, the B-spline transformations, and group by B-spline transformation interactions so that we could estimate a trajectory for each group. These mixed effects models included a random intercept (i.e., random site effect). Contrasts were constructed within each model and were used to estimate the change in adherence for each group from February 2021 – November 2021 and the difference in adherence change between the groups, which was our hypothesis test of interest. These estimated differences in change were reported with 95% confidence intervals (CIs). For both estimates, the difference in change was calculated as the AF group minus the IAU group.

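### Optional improvement: Holm's step-down instead of the fixed 0.025 split keeps family error at or below 5% and raises power per primary outcome from 80% to about 84–86% at the design difference

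*Protocol*

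**What the plan says.** Protocol C7.a names two primary outcomes, sui2 (secondary screen) and csra1 (CSRE), and fixes the level for each: "As there are two primary EPRP outcomes (sui2 and csra1), alpha is set to 0.025". At that level it gives "80% power to detect a difference in change between A/F and IAU of 0.059, and 0.055, respectively", for the two recruitment scenarios in which "N=112 and N=126 are eligible for randomization at R1".

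Protocol C7.b models each outcome by linear regression, bases inference on the group coefficient, and states that "97.5% confidence intervals (CI) will be reported (alpha=0.025"). Nothing in C7 passes alpha from one outcome to the other. The 80% is per outcome. The protocol gives neither the power to confirm both nor a correlation between them.

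The SAP's Primary Aim section analyses two corresponding measures (eCSSRS1 and eCSRE1) with spline mixed models. It states: "These estimated differences in change were reported with 95% confidence intervals (CIs"). It has no 0.025 split and no other multiplicity rule.

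**The concern.** Testing each of two outcomes at 0.025, whatever the other shows, is single-step Bonferroni. Holm's procedure tests the smaller p-value at 0.025 and, if that passes, the larger at 0.05. It controls the family error at 5% under any dependence, rejects everything the fixed split rejects, and sometimes rejects more. It needs only the two p-values, so it works with the protocol's regression and with the SAP's contrasts.

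What the fixed split gives up is the case where one outcome is clearly positive and the other has a p-value between 0.025 and 0.05. The split leaves the second outcome unconfirmed and Holm confirms it. A real effect on both the secondary screen and the CSRE is therefore more likely than necessary to be declared on only one of them.

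**Working it through.** **Inputs**
- Alpha per outcome is 0.025 (C7.a). A 97.5% interval (C7.b) corresponds to a two-sided test at 0.025.
- SD is 0.10 for both outcomes: a similar measure was "used to obtain an estimated standard deviation for sui2 and csra1 of 0.10" (C7.a).
- Sites number 112 or 126 (C7.a). Allocation is 1:1 (C5.b: "will be randomized 1:1 (R1) to receive A/F or continued IAU for 10 months"), so there are 56 or 63 per arm.
- The test is a two-sample t-test (C7.a).
- The correlation between the outcomes is not given. I use 0 to 0.9 as an assumed range.

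**1. Reproduce the stated detectable differences.** The normal approximation is (z₀.₉₈₇₅ + z₀.₈₀) × SD × √(2/n), with z-sum 2.241 + 0.842 = 3.083.
- n = 56: 3.083 × 0.10 × √(2/56) = 0.0583. The noncentral t gives 0.0589, against 0.059 stated.
- n = 63: 3.083 × 0.10 × √(2/63) = 0.0549. The noncentral t gives 0.0555, against 0.055 stated.

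Power by t-test at the stated differences is 80.1% and 79.2%. The protocol's figures reproduce.

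**2. Power of one outcome at 0.05.** When power is 80% at two-sided 0.025, the mean of z is 3.083. At two-sided 0.05 power is Φ(3.083 − 1.960) = 0.8693.

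**3. Independent outcomes, both true effects at the design difference**
- Fixed split, both confirmed: 0.80² = 64.0%.
- Holm, both confirmed. Both p-values must be at most 0.05 and the smaller at most 0.025: 0.8693² − (0.8693 − 0.80)² = 0.7557 − 0.0048 = 75.1%.
- At least one confirmed, either rule: 1 − 0.20² = 96%.
- Holm, per outcome: (0.960 + 0.751)/2 = 85.5%, against 80%.

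With t-test power in place of the normal approximation, the chance of both goes from 64.1% to 75.5% (N = 112, 0.059) and from 62.8% to 74.3% (N = 126, 0.055).

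**4. Correlated outcomes (bivariate normal)**

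| Correlation | Both, fixed split | Both, Holm | Gain (points) | At least one, either rule | Per outcome, Holm |
|---|---|---|---|---|---|
| 0 | 64.0% | 75.1% | 11.1 | 96.0% | 85.5% |
| 0.3 | 66.6% | 76.6% | 9.9 | 93.4% | 85.0% |
| 0.5 | 68.7% | 77.8% | 9.1 | 91.3% | 84.6% |
| 0.7 | 71.3% | 79.4% | 8.1 | 88.7% | 84.1% |
| 0.9 | 75.0% | 81.5% | 6.5 | 85.0% | 83.2% |

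**5. Family error**
- Holm, both nulls true: 1 − 0.975² = 4.94% if independent (the same as the fixed split), and 4.6% by simulation at correlation 0.5.
- Holm, one null true and the other effect at the design value: 4.5% if independent and 4.2% at correlation 0.5 (simulation).
- Two unadjusted 0.05 tests, as the SAP's 95% intervals imply, both nulls true: 1 − 0.95² = 9.75% if independent, and 9.1% by simulation at correlation 0.5.

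**6. Against the SAP's rule.** With the same design effect and independence, two unadjusted tests at 0.05 confirm both with probability 0.8693² = 75.6%, against 75.1% with Holm. Error control would therefore cost about half a point. This comparison borrows the protocol's t-test set-up and is not a power calculation for the SAP's mixed model.

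**The case against.** The protocol contains no error here. C7.a and C7.b agree on a valid, pre-specified rule that controls family error. That stands, and the point is an efficiency gain only.

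A reader might infer from the 80% benchmark, which a site must reach on both the secondary screen and the CSRE, that the trial succeeds only if both outcomes are confirmed, and so that its real power is 64%. The documents do not support this. In C5.a the benchmark is a site-level tailoring variable that decides which randomization a site enters. No section requires both primary tests to succeed, and splitting alpha suggests that either may count alone. If both were required, each could be tested at 0.05 without adjustment, giving 75.6% under independence, slightly more than Holm. Power for both is therefore a supplementary figure, and the chance of at least one success does not change.

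The rise from 64% to 75% is the most favourable case. The measures are consecutive steps of one process at the same sites, so positive correlation is plausible and the gain would be smaller.

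Intervals also matter. Under the fixed split, each 97.5% interval excludes zero exactly when its test rejects. Holm loses that match. Preferring matched intervals is defensible, and this is the real cost of the change.

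Finally, the SAP is dated October 2024, is written in the past tense, and does not use the 0.025 rule. The power gain therefore exists only against the protocol's rule. A reader might infer that Holm would add power to the reported analysis, but it is stricter than two 95% intervals and could add no positive result to theirs.

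**Conclusion.** This is a cheap, optional improvement and not a flaw in validity. Against the protocol's fixed split, Holm keeps family error at or below 5% and is never less powerful. With both true effects at the design difference, power per outcome rises from 80% to about 84–86% for correlations 0 to 0.7 (83% at 0.9). The chance of confirming both rises by 11 points if the outcomes are independent, 9 at correlation 0.5 and 6 at 0.9. The result that Holm is never worse needs no assumption about dependence. The sizes rest on the protocol's SD, a normal model and an assumed correlation.

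Against the SAP the benefit is different. Its unadjusted 95% intervals allow a family error of up to 9.75% under independence, and Holm would restore control at almost no cost in power. The two documents state different rules for the primary aim, so one rule should be set for both.

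**What to change.** - In C7.a–b, state Holm's procedure at family alpha 0.05 on the two primary p-values as the decision rule, and apply the same rule to the SAP's two primary contrasts.
- Keep 0.025 as the planning alpha, so that 0.059 and 0.055 stand as conservative figures. Add the power to confirm both as supplementary, with its correlation assumption.
- Report Holm-adjusted p-values beside the 97.5% intervals, and say that the decision rests on the adjusted p-values.
- Because the SAP was written after the data, disclose the change as post hoc and show the fixed 0.025 result beside it. A second outcome with a p-value between 0.025 and 0.05 would pass Holm but not the protocol's rule, and readers should be able to see that.

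The cost is a sentence or two in each document and no new data or model. The one downside is that the second outcome's 97.5% interval can include zero although Holm rejects, which the reporting sentence must explain.

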Thus, the objective of this national quality improvement project is to develop an adaptive strategy to improve implementation of VA Risk ID to fidelity. Using a sequential multiple assignment randomized trial (SMART) design, two evidence-based implementation strategies will be evaluated: 1) Audit and Feedback (A/F); 2) A/F plus External Facilitation (A/F+EF). We will evaluate these strategies across several domains based on the RE-AIM OUEST mixed methods framework⁹. In addition to focusing on implementation outcomes, such as the impact of these strategies on implementation of VA Risk ID to fidelity, and potential barriers to adopting these strategies, we will also examine the impact of the clinical innovation (i.e., VA Risk ID) on patient-level outcomes. **Primary Aim:** Among sites that do not meet the benchmark for adequate performance (i.e., completion of secondary screening and CSRE for 80% or more of eligible patients) following 6 months of Implementation as Usual (IAU), does the addition of A/F for 10 months significantly improve scores on VA Risk ID performance measures compared to IAU alone? Secondary Aims: 1) Among sites that continue to not meet the benchmark for adequate implementation after 10 months of A/F, does the addition of EF significantly improve scores on VA Risk ID performance measures compared to A/F alone? 2) Among sites that meet the benchmark following A/F alone, is performance maintained following discontinuation of A/F? Outcomes for primary and secondary aims will use clinical performance measures extracted from VA's External Peer Review Program (EPRP) that reflect key practice elements of VA Risk ID: completion of the primary suicide screen, timely completion of the secondary suicide screen and timely completion of the CSRE. Exploratory Aims: 1) Examine the extent to which VA Risk ID is reaching the intended population and compare the characteristics of Veterans reached to all Veterans eligible for screening: 2) Examine contextual factors that may impact the a) implementation of VA Risk ID to fidelity and b) adoption of the implementation interventions. 3) Examine whether Veterans who receive the CSRE are more likely to receive a safety plan than Veterans who screen positive on the primary screen only. **This project directly**

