Secondary Aim 2a. For sites that responded to AF during Phase 1, determine if switching to AF Light during Phase 2 (January 2022 – July 2023) resulted in a significant decrease in eCSSRS1 and eCSRE1 adherence. To determine the effect of switching to AF Light in Phase 2, we compared Group 2 (Continued AF; N=6) to Group 3 (Switched to AF Light; N=6). We used the same approach as was used for the Primary Aim. Monthly eCSSRS and eCSRE adherence was modeled across the entire study period as a function of group (Continued AF and Switch to AF Light), B-spline transformations on time, and group by B-spline transformation interactions, so that we could estimate a trajectory for each group. Knot selection was the same as for the Primary Aim. Contrasts were constructed within each model and were used to estimate the change in adherence for each group from January 2022 – July 2023 and the difference in adherence change between the groups, which was our hypothesis test of interest. These estimated differences in change were reported with 95% Cls. For both estimates, the difference in change was calculated as the Continued AF group minus the Switch to AF Light group.

Secondary Aim 2b. For sites that did not respond to AF during Phase 1, determine if the addition of External Facilitation (EF) during Phase 2 (January 2022 – July 2023) resulted in a significant increase in eCSSRS1 and eCSRE1 adherence. To determine the effect of the addition of EF in Phase 2, we compared Group 4 (Continued AF; N=38) to Group 5 (Added EF; N=17). We used the same approach as was used for the Primary Aim. Monthly eCSSRS and eCSRE adherence was modeled across the entire study period as a function of group (Continued AF and Added EF), B-spline transformations on time, and group by B-spline transformation interactions, so that we could estimate a trajectory for each group. Knot selection was the same as for the Primary Aim. Contrasts were constructed within each model and were used to estimate the change in adherence for each group from January 2022 – July 2023 and the difference in adherence change between the groups, which was our hypothesis test of interest. These estimated differences in change were reported with 95% CIs. For both estimates, the difference in change was calculated as the Continued AF group minus the Added EF group.

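### Both secondary aims are powered on the whole A/F arm, although R2 and R3 divide that arm; the step-down comparison ends up with 6 v 6 sites

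*Protocol*

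**What the plan says.** **Power text (Protocol C7(a)).** Two scenarios are set out, "such that N=112 and N=126 are eligible for randomization at R1". For secondary aim 1 the text takes "facilities eligible for randomization at R2 of 56 and 63, there is 80% power" at differences in change of 0.076 and 0.072, with alpha 0.05 and SD 0.10. Secondary aim 2 is then covered in one sentence: "Given the same assumptions for secondary aim 2 as used for secondary aim 1, the detectable differences in change are the same". No proportion of A/F sites expected to reach the benchmark is given.

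**Randomization (Protocol C5(b)).** R1 allocates sites 1:1 to A/F or continued IAU. For R2, "A/F sites that do not meet the benchmark for adequate implementation at the 10th interventional month will be randomized 1:1". For R3, "A/F sites that meet the criteria for adequate implementation will be randomized 1:1".

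**The question (Protocol Specific Aims, secondary aim 2).** "Among sites that meet the benchmark following A/F alone, is performance maintained following discontinuation of A/F"

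**The analysis (SAP).** Numbering differs: protocol secondary aim 2 is SAP Secondary Aim 2a, and protocol secondary aim 1 is SAP Secondary Aim 2b. Aim 2a asks whether stepping down "resulted in a significant decrease in eCSSRS1 and eCSRE1 adherence", and states: "we compared Group 2 (Continued AF; N=6) to Group 3 (Switched to AF Light; N=6". Aim 2b compares Group 4 (38 sites) with Group 5 (17 sites). The Primary Aim section gives 67 A/F sites in Phase 1.

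**The concern.** An A/F site either meets the benchmark at month 10 or it does not, so it can enter R3 or R2 but not both. If all 56 or 63 sites go to R2, R3 is empty and secondary aim 2 has no data; the reverse also holds. Stating full-arm power for both aims counts the same sites twice.

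What is at stake is mainly secondary aim 2. It asks whether performance holds once A/F is reduced, and the planned test looks for a significant fall. With few sites, a non-significant result is likely even if a real loss of 7 to 8 percentage points occurs. The only power statement a reader can find for this aim is 80% at 0.076/0.072, which would make a null result look far more reassuring than it is. Neither document says a null result would be read as maintenance, but neither rules it out, and no maintenance margin is given.

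**Working it through.** **Inputs.** Two-sample t-test, SD 0.10, alpha 0.05 and 80% power (Protocol C7(a)); 1:1 allocation (C5(b)); site counts from C7(a) and the SAP. Sidedness is not stated. Two-sided 0.05 reproduces the plan's figures; one-sided 0.05 gives 0.067/0.063 and does not.

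**Formula.** Detectable difference = k × SD × √(1/n₁ + 1/n₂). Here k is the noncentrality at which a two-sided 0.05 t-test on n₁ + n₂ − 2 degrees of freedom has 80% power.

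**Step 1: size of the A/F arm.** 112/2 = 56 and 126/2 = 63, the same numbers that C7(a) uses for R2.

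**Step 2: reproduce the plan's figures.**
- 28 v 28: 2.853 × 0.10 × √(1/28 + 1/28) = 2.853 × 0.02673 = 0.0762 (stated 0.076).
- 31 v 32: 2.847 × 0.10 × √(1/31 + 1/32) = 2.847 × 0.02520 = 0.0717 (stated 0.072).

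The same method at alpha 0.025 gives 0.0589 and 0.0555 for R1 (stated 0.059 and 0.055), so the method is identified correctly. The arithmetic is right for its inputs; the inputs cannot both be true.

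**Step 3: divide the arm.** The documents give no responder fraction for planning, so the fractions below are assumptions.

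| A/F sites | Share meeting benchmark | R3 (aim 2) | R2 (aim 1) |
|---|---|---|---|
| 56 | 10% | 0.307 | 0.081 |
| 56 | 25% | 0.163 | 0.089 |
| 56 | 50% | 0.110 | 0.110 |
| 56 | 75% | 0.089 | 0.163 |
| 63 | 10% | 0.307 | 0.076 |
| 63 | 25% | 0.151 | 0.084 |
| 63 | 50% | 0.102 | 0.104 |
| 63 | 75% | 0.084 | 0.151 |

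No split gives the stated figure for both aims. The best that the worse-off aim can do is 0.110 (56 sites) or 0.104 (63 sites).

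**Step 4: the SAP's counts.** 6 + 6 + 38 + 17 = 67, so 12 sites reach the step-down comparison and 55 the facilitation comparison.
- Aim 2, 6 v 6: 3.110 × 0.10 × √(1/6 + 1/6) = 3.110 × 0.05774 = 0.180, which is 2.4 times 0.076 and 2.5 times 0.072. Power is 22% at 0.076 and 20% at 0.072. The 95% CI half-width is 2.228 × 0.05774 = 0.13.
- Aim 1, 55 sites at 1:1 (28 v 27): 2.854 × 0.02697 = 0.077. The double counting costs this aim almost nothing.
- Aim 1, as allocated (38 v 17): 2.854 × 0.02918 = 0.083. This loss comes from the unequal allocation.

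**Step 5: sensitivity to the SD.** The SAP gives no SD for its contrast. The detectable difference scales with SD, so over an assumed 0.05 to 0.15, 6 v 6 gives 0.09 to 0.27. For 80% power at 6 v 6 the SD would have to be 0.10 × 0.076/0.180 = 0.042, or 0.10 × 0.072/0.180 = 0.040.

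**The case against.** - **The figures could be separate best cases.** The text is conditional, and other sections show that small subgroups were foreseen: C5(b) has a rule for fewer than 12 sites at R2, and C7(c) adjusts for region only if numbers permit. But C7(a) does not label the figures as upper limits, and it presents both without saying that one being true makes the other impossible.
- **A non-significant decrease never proves maintenance, even at 28 v 28.** This is correct, and the SAP's 95% CI will show which decreases are excluded. The need for an interpretive sentence therefore does not arise solely from the double counting. The small numbers make it more pressing, because a null result becomes the likely outcome while the document still promises 80% power.
- **The 0.18 mixes the protocol's method with the SAP's counts.** This stands as a limit. The SAP fits monthly mixed spline models to different measures over a longer window, and its step-down arm is AF Light. Sites above 80% may also vary less. As an illustration only, a uniform spread over 0.80–1.00 has SD about 0.058 and would give about 0.10 at 6 v 6, still above 0.076. The SD of change could be larger or smaller than that.
- **The SAP is dated October 2024 and written in the past tense.** A corrected figure will not change recruitment, and the CIs are the proper measure of precision. That limits the remedy to text; it does not make the power statement correct.

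**Conclusion.** The concern holds. It follows from the protocol alone that 80% power at 0.076/0.072 cannot be true for both secondary aims, because R2 and R3 draw on one total of 56 or 63 sites. That conclusion needs no assumption about SD or model.

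The size of the shortfall does rest on assumptions. Under the protocol's t-test with SD 0.10 and the SAP's counts, secondary aim 2 can detect about 0.18 and has 20–22% power at the stated differences. Over an assumed SD of 0.05–0.15 the range is 0.09–0.27. These figures are not the precision of the SAP's mixed model. Secondary aim 1 is essentially unaffected by the double counting (0.077 against 0.076). The primary aim is untouched.

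The 38 v 17 split at R2 is a separate discrepancy with the protocol's 1:1 allocation, and neither document explains it.

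**What to change.** 1. Restate the detectable differences in C7(a) with R2 and R3 as parts of one total: for example 0.110 each if 56 sites divide 28 + 28, and about 0.18 for 6 v 6. Give the responder fraction assumed, and label the figures as based on the two-sample t-test with SD 0.10, not as the precision of the SAP's model.
2. Keep the SAP Secondary Aim 2a test and its 95% CI. Add one sentence: with 6 v 6 sites, a non-significant decrease will not be read as maintained performance.
3. Separately, reconcile 38:17 with 1:1 allocation at R2, and confirm that Groups 4 and 5 are analysed by their R2 assignment.

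The cost is text only: a corrected power statement, one interpretive sentence and an explanation of the R2 allocation. No test or model changes.
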